Until now, laser lithotripsy during ureteroscopy (URS) has been performed using Holmium: yttrium-aluminum-garnet laser. Recently, a new Thulium laser has been introduced. The pulsed infrared light emitted by the Thulium laser has a wavelength of 1940 nm which is close to the water absorption peak, and the energy delivered by the Thulium laser is therefore highly absorbed by water. High water absorption corresponds to low threshold for tissue ablation and stone lithotripsy ¹. The Thulium laser is therefore expected to be very efficient at disintegrating stones. Previous studies have predicted Thulium laser lithotripsy to be up to four times faster than Holmium laser lithotripsy using the same energy settings ². In theory, as the threshold for tissue ablation is low, ureteral lesions caused by unintentional laser firing at the mucosa may result in less bleeding than with holmium lasers as bleeders are instantly coagulated. In addition, the Thulium laser has the advantage of having smaller laser fibers enabling better irrigation during URS.

As the first hospital in Europe, HUH got access to the new Olympus Soltive Premium SuperPulsed Thulium Laser System in June 18th 2020. To date, approximately 30 procedures have been performed using this laser at our hospital, and the preliminary results seem promising.

The laser has been shown to be a highly efficient tool in the treatment of both ureteral and renal stones even at very low energies. Stone burden up to 3.2 cm has been effectively cleared. Our impression is that the laser produces significantly smaller fragments and finer dust-particles compared to the Holmium laser in shorter time. Fragmenting at a setting of 0.6 - 0.8 J at 30 Hz (18 - 24 W) produces dust and disintegrates stones faster than dusting at 0,1 - 0,2 J at 200 - 240 Hz (20 - 48 W), even though the latter setting results in finer dust. Complete disintegration of a 1 cm stone at 0,6 J at 30 Hz has been achieved in less than 20 minutes.

A remarkable characteristic noted when breaking ureteral stones at low energy, is the absence of retropulsion.

No significant intraoperative complications have been registered so far. However, in a few cases small superficial mucosal laser lesions were noted. No bleeding impairing endoscopic vision has been registered, and adequate vision was maintained in all without the use of irrigation pumps. Insertion of a JJ-stent post endoscopically also seems to be required in a few cases only.

Although the preliminary results of the new Thulium laser look promising, there are no clinical randomized trials comparing it to the Holmium laser, which is the current standard laser used for URS lithotripsy.

Aims of the study:

The primary aim of the study is to compare the stone free rate (SFR) following URS lithotripsy with Holmium and Thulium lasers. SFRs will be compared both for ureteral stones, renal stones and ureteral and renal stones in total.

Secondary aims are to compare the results of the two lasers in terms of operating times, intraoperative complications, postoperative complications and the rate of post endoscopic JJ-stenting.

Hypothesis:

1. The SFR, defined as no residual fragments detected on CT scan 3 months after the URS, is higher following lithotripsy with Thulium laser compared to Holmium laser. The corresponding H_0 is that "*there is no difference in SFR following laser lithotripsy with the two lasers.*"
2. Operating time following Thulium laser lithotripsy is shorter compared to Holmium laser. H_0 : "*There is no difference in the operating time between the two laser machines.*"
3. There are less intraoperative complications during Thulium laser lithotripsy compared to Holmium laser. H_0 : "*There is no difference in intraoperative complications between the two laser machines.*"
4. There are less postoperative complications (infections, readmissions, strictures) during Thulium laser lithotripsy compared to Holmium laser. H_0 : "*There is no difference in postoperative complications between the two laser machines.*"
5. Fewer patients will need post endoscopic insertion of JJ-stent following Thulium laser lithotripsy compared to following Holmium laser lithotripsy. The corresponding H_0 is that "*there is no difference in the frequency of post endoscopic JJ-stent placement following laser lithotripsy with the two lasers.*"

Study design:

The study is planned performed as a prospective randomized trial. All patients ≥ 18 years scheduled to URS lithotripsy at the day surgery unit at HUH are invited to be enrolled in the study. After written informed consent, patients are randomized to URS lithotripsy with either Holmium laser or Thulium laser.

Randomization:

The randomization is performed electronically with the same number of patients in each group. The results of the randomization are being kept in sealed and consecutively numbered envelopes that is opened just before starting the endoscopic procedures in each patient.

Patients and data sampling:

All patients ≥ 18 years scheduled for URS lithotripsy at the day surgery unit at HUH are basically eligible for inclusion in this study. Patients with either ureteral stones, renal stones or both can be included. The number of patients/procedures needed to be included in the study is specified in the Power analysis-section below.

The following data need to be registered:

- *Preoperative status:* Age, sex, ASA-status, indication for surgery, earlier surgery for same stone, stone status, acute/planned surgery, prestenting-status, infection.
- *Peroperative characteristics:* Randomization status, primary surgeon, antibiotic prophylaxis, operating time, need for safety guide wire and access sheath, type of endoscope (semi-rigid/flexible), balloon dilatation, impacted stone, successful access to the stone, laser modality, laser settings, laser time and energy used, dusting or fragmentation, retrieval of fragments or left for spontaneous passage, surgeon's assessment of post

- endoscopic stone free status, complications, placement of JJ-stent.
- *Postoperative status:* Length of hospital stay, immediate complications that need urgent treatment, complications after discharge requiring readmission, 3-months follow-up with CT scan (SFR, stricture rate).

The data will be plotted in a registration form which will be available both electronically and on paper. If paper form is used, the data will be registered electronically subsequently and the paper-form maculated. Completed registration-forms are transferred to a SPSS database for statistical analyses.

The registration-forms and the database will be stored at Helse-Bergen's scientific and research server in a designated file assigned from the Data Protection Officer. An ID-Key file combining personal ID to the registration form will be stored at a designated server for this purpose at Helse-Bergen's research servers. Only the project manager ([name]) will have access to this ID-Key file.

The registration forms and the ID-Key file will be kept on the server for five years after the study has been completed in accordance with the law. After five years the data will be made anonymous in terms of deleting the ID-Key file.

Power analysis:

In an earlier study, we found the 3-months SFR after Holmium laser URS lithotripsy to be 54.2% using a strict definition of *no* residual fragments detected on CT scan³. Although this is a strict definition, it leaves no room for personal judgement whether a patient is stone free or not. The definition is therefore suitable for this study purpose.

We expect the Thulium laser to be more efficient in clearing stones than the Holmium laser, with a total SFR of around 80% after URS lithotripsy using this laser.

Comparison of the SFRs between Holmium and Thulium laser will be done using the χ^2 -test. An effect size of 0.3 is considered appropriate assuming the SFRs after Holmium and Thulium laser lithotripsy to be 54.2% and 80%, respectively. The α error probability is set to 0.05 and the power (1- β error probability) is set to 0.8. Comparison of the SFRs following URS with the

two lasers with χ^2 -test is based on a 2 x 2 table, and in this case with only 1 degree of freedom (Df).

Using G*Power, version 3.1.9.4 for power analysis, the total sample size is calculated to be 88. To compensate for possible non-evaluable patients, a total of 120, i.e. 60 patients in each group, are planned to be included in the study.

Statistical analyses:

Statistical analyses will be performed using IBM SPSS Statistics 25 or higher (IBM, Armonk, NY). A p -value < 0.05 will determine statistical significance.

Continuous variables will be compared using independent-samples t -tests, or in the cases where a normal distribution is not met, Mann-Whitney U test. Exact chi-squared test and Fisher's Exact test are used comparing categorical variables.

Ethical considerations, ethical approval and patient consent

Holmium laser lithotripsy is the gold standard during URS today and is in use worldwide. Preliminary results with the new Thulium laser seem promising, however, no randomized trials comparing the outcome of the two laser modalities exists. The planned study therefore seems to be highly clinically relevant. In addition, the new Thulium laser is approved for use during endoscopic lithotripsy and the patients should therefore not be exposed to extra risk of harm using this laser.

Applications for approval by The National Committees for Research Ethics in Norway and The Data Protection Authorities at HUH will be sent prior to study start. In addition, the study will be registered in the clinical research database for randomized trials, ClinicalTrials.gov.

All patients eligible for inclusion in the study will receive oral and written information. Participation in the study is voluntarily, and the patient can choose to withdraw at any point during the study process. Inclusion in the study will only be done after the consent form is signed. The patient information and consent form used for this purpose is obtained from The National Committees for Research Ethics in Norway's website (https://helseforskning.etikkom.no/frister/malforinformasjonsskriv?p_dim=34672).

Laser settings

The laser settings in the two study groups need to be standardized. The following laser settings are suggested as the start-up settings. In the cases of insufficient effect, higher energies can be applied but then need to be registered.

Ureteral stones: 0.4 J at 6 Hz (2.4 watts), long pulse

Renal stones: 0.4 - 0.8 J at 6 - 20 Hz (2.4 - 16 watts) for Holmium and
0.6 - 0.8 J at 30 Hz (18 - 24 watts) for Thulium.

The initial settings for the Thulium laser when treating renal stones are at a higher watt-level compared to the Holmium laser settings, and is therefore expected to be more efficient. However, the fact that the Thulium laser is able to deliver more energy needs to be considered when comparing the clinical outcome of the two lasers.

Study progress

The date for completing the data registration form, patient information and consent form, and application for approval by The National Committees for Research Ethics in Norway is set to 18th of August 2020.

During August 2020 the application form to The Data Protection Authorities at HUH will be sent. Prior to study start the study will also be registered in the clinical research database for randomized trials, ClinicalTrials.gov.

Inclusion of patients and ureteroscopies is expected to start in October 2020, and the inclusion is expected to close during March 2021.

Data analyses and writing a draft is set to spring 2021. Final manuscript ready for submission is planned during the summer 2021.

Funding

No external funding is planned. Hopefully, the project can be completed during regular working hours at Haukeland University Hospital and the University of Bergen.

Conflicts of interest

[name] is a consultant for Olympus, who was not involved in the design, collection, analyses, interpretation or reporting of the data. The two other authors have nothing to disclose.

Publication of data

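### The plan compares the lasers separately in ureteral and renal stones but has no comparison of the two effects; a pre-specified contrast and a reading rule would be a cheap improvement

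*Combined protocol and SAP*

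**What the plan says.** Aims of the study puts three comparisons of the stone-free rate (SFR) inside the primary aim: "SFRs will be compared both for ureteral stones, renal stones and ureteral and renal stones in total". Hypothesis 1 and its null concern SFR overall, and no hypothesis says that the effect differs by location.

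Power analysis rests on one 2 x 2 table. The Holmium rate is from the investigators' own earlier study ("we found the 3-months SFR after Holmium laser URS lithotripsy to be 54.2"%), and Thulium is expected to do better, "with a total SFR of around 80% after URS lithotripsy using this laser".

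Statistical analyses lists t-tests, Mann-Whitney, exact chi-squared and Fisher's exact tests with one significance threshold, 0.05. It contains no interaction or homogeneity test, no model, and no rule for reading location results.

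Laser settings gives one start-up setting for ureteral stones but different renal start-up ranges by laser (2.4–16 W for Holmium, 18–24 W for Thulium). It notes that "The initial settings for the Thulium laser when treating renal stones are at a higher watt-level compared to the Holmium laser settings", and that Thulium's capacity to deliver more energy "needs to be considered when comparing the clinical outcome of the two lasers".

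Patients and data sampling admits patients with ureteral stones, renal stones or both. It gives no expected mix, and Randomization mentions no stratification by location.

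**The concern.** Whether the laser effect differs by location is a natural question here, because the start-up settings differ between lasers for renal stones only. The plan invites the question and supplies nothing that answers it. Two separate p-values cannot: one below 0.05 and one above may arise from the same underlying effect when each group is small. With significance as the only stated criterion, a reader could take such a split as evidence that Thulium works in one location and not in the other. At stake is the interpretation of the location results. The main comparison is unaffected.

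**Working it through.** **Inputs.** From Power analysis: SFR 54.2% (Holmium) and 80% (Thulium), effect size 0.3, alpha 0.05, power 0.8, 88 patients required, 120 planned, equal arms. Assumed, because the plan gives no figure: an even ureteral–renal split, non-overlapping groups, and the same true effect in both locations.

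**The plan's own figure.** Chi-squared on 1 df with w = 0.3: noncentrality = N × 0.3². At N = 88 this is 88 × 0.09 = 7.92, giving power 0.804; at N = 87 power is 0.799. So 88 reproduces, for the total comparison.

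**Power per location.** An even split gives 88/4 = 22 or 120/4 = 30 patients per arm per location. Power comes from exact enumeration of the two binomials at 54.2% and 80%. Power analysis names the chi-squared test for SFR, while Statistical analyses names exact chi-squared and Fisher's tests. The table therefore shows the uncorrected chi-squared and Fisher's tests. With power p in each location:
- exactly one significant = 2p(1 − p)
- both significant = p²
- neither significant = (1 − p)²

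| Evaluable | Test | p | Exactly one | Both | Neither |
|---|---|---|---|---|---|
| 88 | Chi-squared | 0.440 | 2 × 0.440 × 0.560 = 49% | 19% | 31% |
| 88 | Fisher | 0.328 | 2 × 0.328 × 0.672 = 44% | 11% | 45% |
| 120 | Chi-squared | 0.570 | 2 × 0.570 × 0.430 = 49% | 32% | 18% |
| 120 | Fisher | 0.468 | 2 × 0.468 × 0.532 = 50% | 22% | 28% |

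**Uneven split.** With powers A and B, exactly one = A(1 − B) + B(1 − A). Across both sample sizes and both tests this is 46–52% at 60:40, 49–57% at 70:30 and 54–64% at 80:20.

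**Smaller uniform effect** (chi-squared, even split, 88 and 120 evaluable):
- Thulium 75%: 41% and 47%
- Thulium 70%: 30% and 36%
- Thulium 65%: 19% and 23%
- no effect: 9% and 10%

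**Direct contrast.** The standard error of the difference between the two SFR differences is √[2 × (0.542 × 0.458 + 0.8 × 0.2)/n].
- n = 22: SE 0.193, 95% CI half-width 1.96 × 0.193 = 0.38.
- n = 30: SE 0.165, half-width 1.96 × 0.165 = 0.32.

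In simulation under a uniform effect with an even split, a Wald test of this contrast signals a difference in about 6% of trials. Its power to detect 25.8 points (80 − 54.2) in one location against none in the other is only 27% (88 evaluable) or 35% (120).

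**The case against.** A reader might infer that the plan would draw a false location-specific conclusion about half the time. The documents do not support that. No section says that split p-values will be read as a location effect, and both the hypothesis and the sample size concern the total. The percentages describe a pattern of p-values, and the risk lies in how it is read. "About half" also depends on the optimistic planned effect and on an assumed split. Patients with both stone types make the assumption of two independent groups an approximation. All of this stands.

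It can also be said that the contrast has low power and may itself be misread as showing equal effects. That is true, and the plan must say so. But an interval of ±32 to 38 points shows how little the trial can say about location, and two separate p-values conceal that.

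A reader might further hope to settle the energy question by setting ureteral results (common settings) beside renal results (different settings). The documents do not support this either. The settings are start-up values that may be raised, so delivered energy may differ between arms in ureteral cases too. Location is not randomised, so the comparison mixes settings with everything else that differs between locations. Adjustment for delivered energy, a post-randomisation variable, is not proposed in the plan and should not be read into it.

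**Conclusion.** The point holds as a cheap improvement to analysis and reporting. The plan makes location-specific comparisons part of its primary aim and has no method for comparing the effects. Under the planned effect, an even split and non-overlapping groups, exactly one location would be significant in about 44–50% of trials although the effects are identical. The figure rises with a more uneven split and falls with a smaller effect. Nothing in the plan guards against misreading that pattern, but nothing commits to the misreading. The main SFR test is untouched.

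The stated power of 0.8 should not be carried over, to the locations or as the power achieved for the total. It belongs to w = 0.3. At 54.2% against 80% with 88 evaluable patients, power for the total is about 76% by chi-squared and 67% by Fisher's test.

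**What to change.** Add to Statistical analyses:

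- The total SFR comparison is the main test; the ureteral and renal results are exploratory.
- Each location's SFR difference is reported with a 95% CI.
- Locations are compared by the difference between the two SFR differences, on the risk-difference scale only, with a 95% CI. No location-specific claim is made from separate p-values, and a non-significant contrast is not read as equal effects.
- Location is classified from preoperative imaging before the envelope is opened. The background section gives a reason: "A remarkable characteristic noted when breaking ureteral stones at low energy, is the absence of retropulsion". Stone movement during the procedure may therefore depend on the laser. Stone status is already on the preoperative registration list, though location is not spelled out.
- Patients with both stone types stay in the total and form their own category, outside the ureteral–renal contrast.
- The sample size was calculated for the total only. This should be stated without giving 80% as the achieved power.

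The cost is a few sentences and one precise preoperative field, with no extra patients, visits or change to treatment. The drawback is the imprecision of the contrast. Leaving out patients with both stone types will widen its interval further.

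### Hypothesis 5 speaks of need for a JJ-stent, but the outcome is placement, apparently decided by an operator who knows the laser and without listed indications

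*Combined protocol and SAP*

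**What the plan says.** The lead sentence of Hypothesis 5 (section Hypothesis) is about need: "Fewer patients will need post endoscopic insertion of JJ-stent following Thulium laser lithotripsy compared to following Holmium laser lithotripsy". Its null hypothesis is about placement: "there is no difference in the frequency of post endoscopic JJ-stent placement following laser lithotripsy with the two lasers". The secondary aims (Aims of the study) also name a rate of stenting: "postoperative complications and the rate of post endoscopic JJ-stenting".

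Under Randomization, the allocation is kept in "sealed and consecutively numbered envelopes that is opened just before starting the endoscopic procedures in each patient". No blinding is described, and under Laser settings the renal start-up settings differ between the lasers.

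Under Patients and data sampling, the peroperative items end with "endoscopic stone free status, complications, placement of JJ-stent". No reason or indication for a stent is named there, and no other section lists indications. Related items are registered: preoperatively "acute/planned surgery, prestenting-status, infection", and peroperatively the primary surgeon, balloon dilatation, stone impaction, access to the stone, and whether fragments were retrieved or left.

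The opening background section gives the team's impression after about 30 Thulium procedures: "Insertion of a JJ-stent post endoscopically also seems to be required in a few cases only". It also reports: "However, in a few cases small superficial mucosal laser lesions were noted".

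**The concern.** Need and placement are different quantities, and nothing in the plan links them. Whether to leave a stent often involves judgement. Here the decision comes after the laser is known, in a team that has already written down an expectation of few stents with one of the lasers. Randomization balances the patients at baseline. It does not balance a decision taken once the allocation is open.

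For the stone-free rate the plan deliberately chose a definition that removes personal judgement (Power analysis). Nothing similar is said for stenting.

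What is at stake is the wording of one of five numbered hypotheses. If placements differ, the report could say that fewer patients needed a stent when the data show only that fewer received one. Whether a stent was indicated in a patient who left without one is hard to establish afterwards.

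**Working it through.** **1. Need against placement.**

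| Place in the plan | Quantity |
|---|---|
| Hypothesis 5, lead sentence | need |
| Hypothesis 5, null hypothesis | frequency of placement |
| Secondary aim | rate of stenting |
| Data item | placement |

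Three of the four agree. Only the lead sentence claims more than the data can show.

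**2. Who decides, and knowing what.** That the operator knows the laser follows from the timing of the envelope and the laser-specific settings. That the operator decides on the stent is an inference from its listing as a peroperative item; no section says so.

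**3. What the registered items can show.** Prestenting, surgeon, dilatation, impaction, access, complications and fragments left describe the case. None says whether a stent was indicated.

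**4. How much a small shift could matter.** The plan gives no stent rate, so there is no figure of its own to reproduce. Its total of 88 concerns the stone-free rate and is not used here. From the plan come 60 patients per arm (Power analysis), Fisher's exact test and p < 0.05 (Statistical analyses). Taken here as assumptions are a two-sided test, all stent rates and all shifts.

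With Holmium count X ~ Bin(60, p_H) and Thulium count Y ~ Bin(60, p_T),

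P(significant, favouring Thulium) = Σ P(X = x)·P(Y = y), summed over all pairs with y < x and Fisher p < 0.05.

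Let true need be equal, so that p_H = need and p_T = need + shift. A shift of 5 points is 0.05 × 60 = 3 patients.

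| Equal need | No shift, favours Thulium | Thulium 5 points lower, favours Thulium | Thulium 5 points higher, favours Holmium |
|---|---|---|---|
| 10% | 1.1% | 8.8% | 7.7% |
| 20% | 1.4% | 6.8% | 6.2% |
| 30% | 1.5% | 6.0% | 5.7% |
| 40% | 1.6% | 5.6% | 5.8% |
| 50% | 1.8% | 5.9% | 5.9% |

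With Thulium 10 points lower, at need of 20%, 30%, 40% and 50%, the chance of favouring Thulium is 24.7%, 18.1%, 15.4% and 15.5%.

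For scale, against 24 of 60 Holmium stents (40%), Thulium would need 13 or fewer of 60 for significance, a gap of 24 − 13 = 11 patients. A shift of 3 patients seldom produces that alone.

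**5. Why unstented patients must be recorded.** Suppose an indication is present in 40% of each arm (0.40 × 60 = 24 patients) and 3 indicated Thulium stents are withheld, so that 21/60 = 35% are placed. Counting only placed stents that had an indication compares 40% with 35% and favours Thulium in 5.6% of trials. Counting indications present compares 40% with 40% and gives 1.6%. The contrast holds only if indications are recorded faithfully. A reason noted for placed stents alone would miss the withheld ones.

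**The case against.** The strongest reply is that the tested endpoint is already right. Placement by randomized laser is a legitimate pragmatic outcome: it is what happens when this laser is used, and an operator cannot be blinded to it. This stands. The gap lies in the lead sentence and in the missing common indications, not in the open design.

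Second, the gap may be partly closed in a document that is not available. The protocol is dated 5 August 2020 and the registration form was due by 18 August 2020, so the form may ask for a reason. This also stands. One can say only that the protocol names none.

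Third, a reader might infer from the recorded mucosal lesions that caution with Thulium would distort the comparison and hide a real benefit. In the same model, with need truly 20 points lower than a Holmium rate of 30%, 40% or 50%, raising Thulium placements by 5 points cuts power from 73%, 60% or 54% to 42%, 34% or 32%. The documents do not support calling that loss bias. A stent placed because the laser injured the mucosa is a genuine effect of the laser and belongs in the outcome. Only caution with no finding behind it would be bias.

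Fourth, the surgeon who would record the indication also knows the laser, so expectation can move that record too. This stands, and it is why a supporting significance test on indications is not worth adding. A list agreed beforehand still makes visible the stents placed outside it and those withheld despite it.

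**Conclusion.** The point holds as a limit on interpretation, with an inexpensive change to conduct. A difference in placements may partly reflect operator expectation and should not by itself be reported as a difference in need. The placement null hypothesis remains testable, and the CT-based stone-free endpoint and the sample size are untouched.

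The illustrated size is modest. At an assumed 5-point shift, about 6–9% of trials would wrongly favour Thulium, against 1–2% with no shift, so most such trials would show nothing. Larger assumed shifts give larger figures, but the documents contain nothing on which to base any shift.

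A reader might infer that the stent comparison is biased towards Thulium, or is invalid. The documents support neither. The stated expectation points towards fewer Thulium stents, the observed lesions could lead to more, and neither the direction nor the size of any bias is established. The conclusion rests on the inference that the operator decides, and on the registration form not already recording indications.

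**What to change.** Before the first inclusion (expected in October 2020):

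1. Agree one short written list of stenting indications for both arms, its content set by the investigators. Deviations are allowed if recorded.
2. Unless the form already has it, add a field completed at the end of every procedure, for stented and unstented patients alike: whether a listed indication was present and which one, and whether a stent was placed.
3. In Hypothesis 5, replace need by receive. Keep all placements as the outcome.
4. Tabulate by arm, descriptively and without a further significance test, the stents placed without a listed indication and those withheld despite one.
5. If placements differ, report a difference in placements and read it beside that table. Do not report it as a difference in need.

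The cost is a short agreement among the surgeons, one form field for 120 patients and one table, with no extra procedure or visit. Surgeons lose a little freedom. Some bias remains because the same unmasked surgeon records the indication, so the table can be consistent with lower need but cannot prove it.

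### Allocation and the total SFR test both ignore stone location, so a chance imbalance can shift the total SFR difference by a few points; stratifying by location is a cheap, modest improvement

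*Combined protocol and SAP*

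**What the plan says.** - **Allocation** (Randomization): "The randomization is performed electronically with the same number of patients in each group". The results are held in "sealed and consecutively numbered envelopes that is opened just before starting the endoscopic procedures in each patient". No strata, blocks or minimisation are described, and no separate envelope series by stone location.
- **Primary aim** (Aims of the study): "SFRs will be compared both for ureteral stones, renal stones and ureteral and renal stones in total".
- **Population** (Patients and data sampling): "Patients with either ureteral stones, renal stones or both can be included". Stone status is on the list of preoperative data. The expected mix of locations is not given.
- **Assumed rates** (Power analysis): 54.2% for Holmium, from an earlier study at the hospital, and for Thulium "with a total SFR of around 80% after URS lithotripsy using this laser". Both are pooled over locations.
- **Test** (Power analysis; Statistical analyses): SFR is compared with a chi-square on a 2 x 2 table. Exact chi-squared and Fisher tests are named for categorical variables. No stratified or adjusted analysis is mentioned.
- **Settings** (Laser settings): start-up settings are given by location. The ureteral line, "Ureteral stones: 0.4 J at 6 Hz (2.4 watts), long pulse", does not distinguish the lasers. The renal ranges are 2.4-16 W for Holmium and 18-24 W for Thulium.

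**The concern.** The plan treats stone location as important enough to split its primary aim, and location can be established before the envelope is opened. But neither the allocation nor the analysis of the total uses it. If one location clears more easily than the other, an arm that happens to receive more of the easier stones gains SFR points that have nothing to do with the laser, and an unadjusted 2 x 2 test cannot remove them.

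In a single-hospital trial of 120 patients, one unlucky draw would be awkward to explain. A location-adjusted analysis chosen after seeing the data would look post hoc. Allocation can be stratified only if this is settled before enrolment starts.

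**Working it through.** **Inputs.** From the protocol: 60 per arm, SFR 54.2% and 80%, two-sided alpha 0.05. Assumed, because the documents are silent: a ureteral share q of 30-70% and an SFR gap g between locations of 10-35 points.

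**The plan's own figure.** "An effect size of 0.3 is considered appropriate". With w = 0.3, 1 df, alpha 0.05 and power 0.80, the noncentral chi-square gives N = 88, as stated. The quoted rates themselves give w = 0.258 / (2 × √(0.671 × 0.329)) = 0.275 and N = 105. That is a separate matter. At the planned 60 per arm, power for 54.2% against 80% is about 86-87%.

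**Size of a chance imbalance.** With m = 120q ureteral patients and fixed arms of 60, the number x in the Thulium arm is hypergeometric:

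- SD(x) = √(60 × q(1 − q) × 60/119), which is 2.52 at q = 0.3 or 0.7 and 2.75 at q = 0.5.
- SD of the between-arm difference in ureteral share = 2 × SD(x)/60, which is 8.4 to 9.2 points.

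**Shift in the total SFR difference.** Shift = g × (2x − m)/60, so its SD is g times 8.4-9.2 points:

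| Assumed gap g | SD of shift (points) |
|---|---|
| 10 points | 0.8-0.9 |
| 25 points | 2.1-2.3 |
| 35 points | 2.9-3.2 |

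At the top of the range the 95% limits are 1.96 × 3.2 = ±6.3 points. For gaps of 25-35 points, a shift of 5 points or more in either direction occurs in about 3-10% of trials.

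**Error rate of the planned total test** (simulated with no true effect, 60 patients in each location, uncorrected chi-square):

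- Over all randomisations: about 5.4% two-sided, and 2.7% in favour of Thulium.
- Given a 35:25 ureteral split favouring Thulium: 6.5% (25-point gap) to 8.5% (35-point gap) in favour of Thulium, against 2.3% and 2.0% at 30:30. Here the shift is g × 10/60, or 4.2-5.8 points. A split at least this uneven has probability 0.10 in either direction, so about 0.05 in Thulium's favour.

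**Within-location comparisons.** These hold location fixed. Take simulated trials in which Thulium received at least 20 points more renal patients (about 2% of trials; 30-point gap; Holmium SFR 69.2% ureteral, 39.2% renal):

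| Comparison | Mean difference, no effect | Mean difference, planned effect |
|---|---|---|
| Total | −6.7 | 19.3 (planned 25.8) |
| Renal only | −0.1 | 25.8 |
| Ureteral only | −0.2 | 25.9 |

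The type I error within location in those trials is 4.9% and 4.8%. Uneven arm sizes cost only precision. For 54.2% against 80%, a 60-patient subgroup split 36:24 has power 0.54-0.57 against 0.57 when even. A 36-patient subgroup split 24:12 has 0.31-0.37 against 0.37. Over all randomisations, stratified against unstratified allocation gives 0.53 and 0.53 for renal stones, and 0.80 and 0.79 for ureteral stones.

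**Effect of the change on the total** (equal location shares, gaps of 25-35 points, Thulium averaging 80% with a common odds ratio across locations). Stratified allocation with the planned Pearson test becomes conservative, with error 4.0-4.7%. A Cochran-Mantel-Haenszel test brings error back to about 5% and raises power from about 87% to 88-90%, a gain of about 1.5-3 points. At gaps of 10-20 points the gain is about 0-1 point.

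**The case against.** The strongest reply is that equal, unstratified allocation in a two-arm, single-centre trial is an accepted design. Randomisation already makes the planned test unbiased, and its overall error of about 5.4% is close to nominal. This stands. The 6.5-8.5% figure holds only after a particular unlucky split and must not be read as the trial's error rate; the opposite split makes a false Thulium result less likely.

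Second, the size rests on an assumed gap. At 10 points the shift has an SD of under 1 point, against a planned 25.8. This also stands, and is why the range is shown.

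Third, a stratified analysis alone would deal with most of the shift without a second envelope series. That is right, but no such analysis is planned.

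Two stronger readings are tempting. A reader might infer that location imbalance distorts all three SFR comparisons. It cannot: within ureteral or renal stones there is no location mix to be unbalanced. What limits those two comparisons is their size (power 0.37-0.57 with 36-60 evaluable patients, evenly split), which stratification does not change. A reader might also infer that the different renal settings make the lack of stratification worse. The Holmium-Thulium difference in settings within renal stones is part of the treatment contrast. Missing stratification does not cause it, and stratification would not remove it. It is a reason why the effect may differ by location.

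**Conclusion.** The point holds for the total SFR only, and as a modest one. The plan fixes total arm sizes and describes no handling of location at allocation or analysis, so in a given trial the total difference can be off by an SD of about 0.8-3.2 points through location mix alone. This is chance imbalance, not systematic bias. The figures depend on the assumed 30-70% ureteral share and 10-35 point gap; the simulated error rates and power gains also assume equal location shares. The documents do not support a claim of inflated overall error or of bias in the ureteral and renal comparisons. It is a cheap improvement that should be decided before the first patient is randomised.

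**What to change.** 1. **Randomization.** State that allocation is 1:1 in permuted blocks of randomly varied size, stratified by preoperative stone location (ureteral only / any renal stone). Use two separately numbered envelope series, or release each allocation from the electronic system.
2. **Statistical analyses.** State that the total SFR is compared with a Cochran-Mantel-Haenszel test stratified by the same two groups. Naming the test matters, because stratified allocation followed by the unadjusted chi-square is conservative.
3. **Classification.** Use the same two groups for the location-specific comparisons, and say explicitly where patients with stones in both sites belong. The plan leaves this open.

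**Cost.** Two lists and envelope series instead of one, prepared before the first patient, and one sentence on analysis. No extra patients are needed. The downside is that staff must draw from the correct series; varied block sizes keep the next allocation hard to guess. If two series are not wanted, items 2 and 3 alone capture most of the gain.
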